4.3 Pharmacokinetics

Pharmacokinetics will be measured using serum concentration-time data (both nivolumab and daratumumab).

4.4 Immunogenicity

Serum samples will be evaluated for development of nivolumab and daratumumab Anti-Drug Antibodies (ADA) by validated assays. Samples may also be analyzed for neutralizing antibodies.

Serum samples collected will be analyzed by a validated immunogenicity assay. Selected serum samples may be analyzed by an exploratory orthogonal method that measures anti-nivolumab.

In addition, ad hoc serum samples designated for pharmacokinetic or biomarker assessments may also be used for immunogenicity analysis if required (e.g., insufficient volume for complete immunogenicity assessment or to follow up on suspected immunogenicity related AE).

Blood samples for immunogenicity analysis will be collected. Samples will be evaluated for development of Anti-Drug Antibody (ADA) by a validated electrochemiluminescent (ECL) immunoassay.

5 SAMPLE SIZE AND POWER

Sample size determination is not based on statistical power calculation.

40 participants were planned to be enrolled to each cohort. In this study, an ORR in excess of 10% will be considered of clinical interest for TNBC and PAC cohort. An ORR in excess of 20% will be considered of clinical interest for NSCLC cohort.

Assuming the true ORR is 25%, 40 participants in each tumor type can provide approximately 79.8% power to reject the null hypothesis that the ORR is 10%, considering a 2-sided alpha of 5%.

Assuming the true ORR is 40%, 40 participants in each tumor type can provide approximately 83.7% power to reject the null hypothesis that the ORR is 20%, considering a 2-sided alpha of 5%.

Table 5.1 shows the precision of the estimation of ORR based on the two-sided 95% exact CI using Clopper-Pearson methods based on 4, 8, 12, 16 and 20 responders out of 40 participants. If at least 9 responses are observed, i.e., $ORR \geq 22.5\%$, the lower bound of the 95% CI excludes 10%. If at least 14 responses are observed, i.e., $ORR \geq 35\%$, the lower bound of the 95% CI excludes 20%.

Table 5-1: Two-sided 95% exact CI using Clopper-Pearson Method Based on the Number of Observed Responses from 40 participants

Number of Observed Responses	4	8	12	16	20
Observed Response Rate	4/40 (10.0%)	8/40 (20.0%)	12/40 (30.0%)	16/40 (40.0%)	20/40 (50.0%)
95% exact CI (%)	(2.8, 23.7)	(9.1, 35.6)	(16.6, 46.5)	(24.9, 56.7)	(33.8, 66.2)

A sample size of 40 can also detect, with more than 87% probability, a safety event that occurs at an incident rate of 5%.

6 STUDY PERIODS, TREATMENT REGIMENS AND POPULATIONS FOR ANALYSES

6.1 Study Periods

- Baseline period:
 - Baseline evaluations or events will be defined as evaluations or events that occur before the date and time of the first dose of study treatment. Evaluations (laboratory test) on the same date and time of the first dose of study treatment will be considered as baseline evaluations. Events (AEs) on the same date and time of the first dose of study treatment will not be considered as pre-treatment events.
 - In cases where the time (onset time of event or evaluation time and dosing time) is missing or not collected, the following definitions will apply:
 - ◆ Pre-treatment AEs will be defined as AEs with an onset date prior to but not including the day of the first dose of study treatment;
 - ◆ Baseline evaluations (laboratory tests) will be defined as evaluations with a date on or prior to the day of first dose of study treatment.
- Post baseline period:
 - On-treatment AEs will be defined as AEs with an onset date and time on or after the date and time of the first dose of study treatment (or with an onset date on or after the day of first dose of study treatment if time is not collected or is missing). For subjects who are off study treatment, AEs will be included if event occurred within a safety window of 30 days (or 100 days depending on the analysis) after the last dose of study treatment. No “subtracting rule” will be applied when an AE occurs both pre-treatment and post-treatment with the same preferred term and grade.
 - On-treatment evaluations (laboratory tests) will be defined as evaluations taken after the day (and time, if collected and not missing) of first dose of study treatment. For subjects who are off study treatment, evaluations should be within a safety window of 30 days (or 100 days depending on the analysis) after the last dose of study treatment.

6.2 Treatment Regimens

For this non-randomized study, analyses will be based on the treatment group “as treated”.

6.3 Populations for Analyses

- All Enrolled subjects: All subjects who signed the informed consent form and obtained a subject number.
- All Treated subjects: All enrolled subjects who received at least one dose of any study treatment. This will be both efficacy and safety population.
- Subjects Entered Follow-up: All subjects who entered the follow-up period as specified in subject status CRF pages.
- All Treated Subjects with Objective Response: All treated subjects with response of CR or PR per RECIST v1.1 per Investigator.

Unless otherwise specified, the efficacy and safety analyses will include all treated subjects.

7 STATISTICAL ANALYSES

7.1 General Methods

Unless otherwise noted, discrete variables will be tabulated by the frequency and proportion of subjects falling into each category, grouped by treatment. Percentages given in these tables will be rounded to the first decimal and, therefore, may not always sum to 100%. Percentages less than 0.1 will be indicated as '< 0.1'. Continuous variables will be summarized by treatment group using the mean, standard deviation, median, minimum, and maximum values.

Time-to-event variables (e.g. time-to resolution) will be analysed using the Kaplan-Meier technique. When specified, the median will be reported along with 95% CI using Brookmeyer and Crowley method¹ (using log-log transformation for constructing the confidence intervals²).

The conventions to be used for imputing missing and partial dates for analyses requiring dates are described in [Section 8](#).

All analyses would be presented by tumor type:

- Triple negative breast cancer (TNBC)
- Non-small cell lung cancer (NSCLC)
- Pancreatic adenocarcinoma cancer (PAC).

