**4. OBJECTIVES AND ENDPOINTS**

**Table 4.-1: Objectives and Endpoints**

Objectives	Endpoints

Primary
 
To establish the tolerability of the combination of nivolumab and daratumumab in participants with advanced or metastatic solid tumors.
	
Incidence of adverse events (AE), serious adverse events (SAE) and specific laboratory abnormalities (worst grade).

Secondary
 
 
• To evaluate the objective response rate (ORR) of nivolumab combined with daratumumab in participants with advanced or metastatic tumors in each cohort.
 
• To assess progression free survival (PFS) of nivolumab combined with daratumumab in participants with advanced or metastatic tumors in each cohort.
 
• To characterize the pharmacokinetics of nivolumab and daratumumab in participants with advanced or metastatic tumors.
 
• To characterize the immunogenicity of nivolumab and daratumumab in participants with advanced or metastatic tumors
 
	
 
• ORR, duration of response (DOR), best overall response (BOR) in each cohort, based on RECIST 1.1 criteria (Appendix 7).
 
• Median PFS in each cohort
 
• Pharmacokinetic parameters, influence of intrinsic and extrinsic covariates and potential exposure-response relationship will be characterized using integrated analyses.
 
• Immunogenicity of nivolumab and daratumumab will be assessed by ADA positivity
 

[REDACTED]
 
[REDACTED]
 
[REDACTED]
	
[REDACTED]

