3.1 Primary

To establish the tolerability of the combination of nivolumab and daratumumab in participants with advanced or metastatic solid tumors.

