3.2 Secondary

- To evaluate the objective response rate (ORR) of nivolumab combined with daratumumab in participants with advanced or metastatic tumors in each cohort.
- To assess progression free survival (PFS) of nivolumab combined with daratumumab in participants with advanced or metastatic tumors in each cohort.
- To characterize the pharmacokinetics of nivolumab and daratumumab in participants with advanced or metastatic tumors.
- To characterize the immunogenicity of nivolumab and daratumumab in participants with advanced or metastatic tumors

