7.1.1 Adverse Events, Serious Adverse Events

Serious adverse events consist of AEs deemed serious by the Investigator and flagged accordingly in the CRF and clinical database.

Adverse events leading to study drug discontinuation are AEs with action taken regarding study drug(s) = "Drug was discontinued".

Adverse events will be coded using the Medical Dictionary for Regulatory Activities (MedDRA), and the most recent version of the dictionary at the time of the database lock will be used. Adverse events results will be graded for severity using NCI Common Terminology Criteria for Adverse Events (CTCAE) version 4.0.

In the AE summary tables, unless otherwise specified, subjects will be counted only once at the Preferred Term (PT), only once at the System Organ Class (SOC), and only once at subject level for the counting of total number of subjects with an AE. The AE tables will be sorted by the SOCs and then PTs. SOC will be ordered by descending frequency overall and then alphabetically. PTs will be ordered within SOC by descending frequency overall and then alphabetically. The sorting will be done based on the 'Any Grade' column of the experimental arm when arms are presented side-by-side.

Unless otherwise specified, the AE summary tables will be restricted to on-treatment events regardless of the causality.

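### The primary tolerability objective covers all treated participants, but the SAP specifies presentation by tumor type and no combined safety estimate

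*SAP*

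**What the plan says.** The primary objective (SAP 3.1, matching Protocol Table 4.-1) reads "To establish the tolerability of the combination of nivolumab and daratumumab in participants with advanced or metastatic solid tumors". Its endpoint is the incidence of AEs, SAEs and specified laboratory abnormalities by worst grade. It names no cohort. The secondary response objective (SAP 3.2) does: "To evaluate the objective response rate (ORR) of nivolumab combined with daratumumab in participants with advanced or metastatic tumors in each cohort". The progression-free survival objective is also set per cohort.

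SAP 7.1 gives the one explicit rule on layout: "All analyses would be presented by tumor type", followed by TNBC, NSCLC and PAC, with no total. SAP 7.5.2 to 7.5.5 (SAEs, AEs leading to discontinuation, all AEs, laboratory tests) name no combined column and no confidence interval.

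Other sentences point less clearly:

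- SAP 6.3: "Unless otherwise specified, the efficacy and safety analyses will include all treated subjects".
- SAP 7.1: "discrete variables will be tabulated by the frequency and proportion of subjects falling into each category, grouped by treatment".
- SAP 7.1.1: "SOC will be ordered by descending frequency overall and then alphabetically".
- SAP 7.5.2 to 7.5.4 call the AE and SAE tables overall summaries, without saying whether that means across cohorts.

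The only sample-size statement about safety is for one cohort (SAP 5): "A sample size of 40 can also detect, with more than 87% probability, a safety event that occurs at an incident rate of 5" (per cent).

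**The concern.** All participants were initially assigned to the same combination, dose and schedule (SAP 2.2; Protocol 7.2), and the objective asks about tolerability of that combination. If the SAP is followed to the letter, the report gives three cohort-specific incidences and no estimate for the population named in the primary objective. The secondary objectives, by contrast, are analysed in the cohorts they name.

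The cohorts are also unequal. TNBC and PAC met their enrollment goals, while fewer than 20 NSCLC participants had been treated when the combination was stopped (SAP, Schedule of Analyses). A rate quoted from one column is imprecise, most of all in NSCLC. At stake is how tightly the close-out report can bound the rate of an uncommon toxicity under the combination.

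**Working it through.** **1. The plan's own figure.** The chance of at least one event among n participants with true rate p is 1 − (1 − p)^n. For p = 5% and n = 40 this is 1 − 0.95^40 = 0.871, which reproduces the stated figure of more than 87%. For n = 19 it is 1 − 0.95^19 = 0.623, so within the NSCLC cohort the figure is at most 62%.

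**2. Inputs.** The documents give no treated count by cohort. The 188 enrolled (Protocol 5.2) are not a treated count, because the protocol defines enrolled participants as all who signed consent. Assumptions:

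- TNBC 40 and PAC 40, because both met goals set at 40.
- NSCLC 1 to 19, because fewer than 20 were treated.
- Combined: 40 + 40 + 1 = 81 up to 40 + 40 + 19 = 99.

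**3. Does splitting the columns hide events?** No. At a true rate of 1% and the largest total, the chance that no column shows an event is 0.99^40 × 0.99^40 × 0.99^19 = 0.99^99 = 0.370. The chance that some column shows one is therefore 63%, exactly the chance for a combined column. Setting the 33% for a single cohort of 40 (1 − 0.99^40) against that 63% compares one cohort with the whole study, not one layout with another.

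**4. Precision.** After zero events, the upper limit of the two-sided 95% Clopper-Pearson interval is 1 − 0.025^(1/n). The last column gives the exact interval when about 10% of participants have an event.

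| Participants | Upper limit, zero events | Interval at about 10% observed |
|---|---|---|
| 19 (NSCLC at most) | 17.6% | 2/19: 1.3 to 33.1% |
| 40 (one full cohort) | 8.8% | 4/40: 2.8 to 23.7% |
| 81 (combined, low) | 4.5% | 8/81: 4.4 to 18.5% |
| 99 (combined, high) | 3.7% | 10/99: 5.0 to 17.8% |

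The interval for 4/40 agrees with SAP Table 5-1.

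**5. Does other wording already require a combined estimate?** SAP 6.3 says who is analysed, and it covers efficacy too. SAP 7.4.3 shows that this does not imply pooling: it sets the aim for all treated subjects and then estimates the survival function separately for each tumor type. SAP 7.1.1 is a sorting rule, and the same paragraph mentions side-by-side arms that this study does not have. Grouping by treatment could mean one group, since all cohorts began on one regimen, but that reading conflicts with the tumor-type rule in the same section. None of these sentences settles the matter.

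**The case against.** The strongest reply is that little is lost. The cohorts do not overlap and each participant is counted once per term, so combined numerators and denominators are column sums. By-subject listings of deaths, SAEs, AEs leading to discontinuation, all AEs and laboratory abnormalities are planned, so a rare serious event stays visible. The table restricted to AEs of at least 5% in any treatment group is also safe: a term that reaches 5% combined must reach 5% in at least one cohort. All of this stands. The choice still changes that table's content. Read per cohort, one NSCLC event qualifies (1/19 = 5.3%); read as one group of 99, five are needed (5/99 = 5.1%).

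The SAP also never says *only*, and SAP 9 refers to a Data Presentation Plan for the mock-ups, which is not among these documents. A total column may already exist there. This stands too, so the finding is an unspecified estimate and not a prohibited one.

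The SAP plans no confidence intervals for safety, so the wide cohort intervals above are not outputs it promises. They measure what a combined estimate would add, and the intervals are a new request.

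A combined column has limits of its own. It averages tumor types with different background event rates. From 13 June 2018 NSCLC participants were to receive nivolumab alone, so an unqualified total could count monotherapy events as combination events. The fix has to deal with both.

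**Conclusion.** The SAP specifies no estimate for the population of its primary objective and leaves open whether one will be produced. A combined estimate would lower the upper limit after zero events to 3.7 to 4.5%, from 8.8% in a cohort of 40 and 17.6% in a cohort of 19. At about 10% observed, the interval would narrow from 2.8 to 23.7% (4/40) to 5.0 to 17.8% (10/99). These figures rest on the assumed treated counts; an NSCLC cohort below 19 would have a wider interval of its own. The combined rate describes the mix of tumor types actually treated.

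A reader might infer three stronger things that the documents do not support:

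- That the SAP forbids pooling. It does not; its wording is ambiguous.
- That tumor-type columns make rare toxicity less likely to be found. Step 3 of the working shows that they do not.
- That the primary objective cannot be answered. The combined counts can be recovered by addition.

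This is a gap in specification and reporting, with no loss of data. It is worth closing because it concerns the primary objective and costs almost nothing.

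**What to change.** In SAP 7.1 and 7.5.2 to 7.5.5:

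- State that summaries of AEs, SAEs, AEs leading to discontinuation and laboratory abnormalities are shown by tumor type and for all treated participants combined, and that the combined column addresses the primary objective.
- Add exact 95% confidence intervals for any AE, any AE of Grade 3 or higher, and any SAE.
- Define *treatment group* and *overall*, and apply the definition to the 5% cut-off in SAP 7.5.4.
- For laboratory rows, use the number of participants tested as the denominator. Amylase and lipase are measured only in PAC (Protocol Table 9.4.4-1). The sentence in SAP 7.5.5 that limits each test's population to participants with the abnormality needs to be aligned with this.
- State how NSCLC events after the switch to nivolumab alone are counted, for example flagged or excluded from the combination estimate. SAP 7.3.1 already plans to count the participants who switched.

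The Data Presentation Plan should be checked against this wording. The cost is a few sentences and one column per safety table, with no new data collection. The total mixes tumor types with different background rates; the retained tumor-type columns keep those differences visible.

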7.1.1 Adverse Events, Serious Adverse Events

Serious adverse events consist of AEs deemed serious by the Investigator and flagged accordingly in the CRF and clinical database.

Adverse events leading to study drug discontinuation are AEs with action taken regarding study drug(s) = "Drug was discontinued".

Adverse events will be coded using the Medical Dictionary for Regulatory Activities (MedDRA), and the most recent version of the dictionary at the time of the database lock will be used. Adverse events results will be graded for severity using NCI Common Terminology Criteria for Adverse Events (CTCAE) version 4.0.

In the AE summary tables, unless otherwise specified, subjects will be counted only once at the Preferred Term (PT), only once at the System Organ Class (SOC), and only once at subject level for the counting of total number of subjects with an AE. The AE tables will be sorted by the SOCs and then PTs. SOC will be ordered by descending frequency overall and then alphabetically. PTs will be ordered within SOC by descending frequency overall and then alphabetically. The sorting will be done based on the 'Any Grade' column of the experimental arm when arms are presented side-by-side.

Unless otherwise specified, the AE summary tables will be restricted to on-treatment events regardless of the causality.

7.1.2 Laboratory Tests

Clinical laboratory parameters (hematology, serum chemistry and thyroid function tests) will be evaluated.

Laboratory tests will be graded using the NCI Common Terminology Criteria NCI CTCAE version 4.0.

Clinical laboratory data will be summarized and listed both using the International System of Units (SI) and US conventional units.

In the laboratory summary tables, unless otherwise specified, subjects will be counted only once for each lab parameter according to their worst on treatment CTC grade (worst being the highest CTC grade).

The laboratory tables and listings will be sorted by laboratory category, laboratory subcategory and laboratory test code sequence number.

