- h) Either a formalin-fixed, paraffin-embedded (FFPE) tissue block or unstained tumor tissue sections, obtained within 3 months prior to first dose, with an associated pathology report, must be submitted to the core laboratory for inclusion. Central lab must provide Interactive Response Technology (IRT) with confirmation of receipt of evaluable tumor tissue prior to study treatment. Biopsy should be excisional, incisional or core needle. Fine needle aspiration is unacceptable for submission. If not enough tumor sample is available, the investigator has to contact the BMS study team to inform the BMS team if less than 25 charged unstained slides are available for the potential impact on biomarker testing.
- i) Prior focal palliative radiotherapy to an isolated bone or soft tissue metastasis must be completed at least 2 weeks before study drug administration.
- j) All baseline laboratory requirements will be assessed and should be obtained within 14 days of first dose. Screening laboratory values must meet the following criteria:
  - i. WBCs  $\geq 2000/\mu\text{L}$  (growth factors not permitted within 1 week of study drug administration; pegylated growth factors not permitted within 3 weeks of first study drug administration)
  - ii. Neutrophils  $\geq 1500/\mu\text{L}$  (growth factors not permitted within 1 week of study drug administration; pegylated growth factors not permitted within 3 weeks of first study drug administration)
  - iii. Platelets  $\geq 100 \times 10^3/\mu\text{L}$  (transfusions not permitted within 72 hours prior to qualifying laboratory value)
  - iv. Hemoglobin  $\geq 9.0 \text{ g/dL}$  (transfusions not permitted within 72 hours prior to qualifying laboratory value; recombinant human erythropoietin not permitted within 3 weeks of study drug administration)
  - v. Estimated creatinine clearance by Cockcroft-Gault formula  $\geq 30 \text{ mL/min}$
  - vi. AST and ALT levels  $\leq 3 \times \text{ULN}$  or  $\leq 5 \times \text{ULN}$  if liver metastases are present

- vii. Total Bilirubin  $\leq 1.5 \times$  ULN (except participants with Gilbert Syndrome who can have total bilirubin  $< 3.0$  mg/dL)
- viii. Albumin  $\geq 3$  g/dL
- ix. For participants with pancreatic adenocarcinoma
  - a. Lipase  $\leq 1.5 \times$  ULN. Participants with lipase  $> 1.5 \times$  ULN may enroll if there are neither clinical nor radiographic signs of a pancreatitis

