### 10.3.2 Safety Analyses

Safety analyses will be performed in all treated participants. Descriptive statistics of safety will be presented using NCI CTCAE version 4.0. All on-study AEs, treatment-related, AEs, SAEs and treatment-related SAEs will be tabulated using worst grade per NCI CTCAE v4.0 criteria by system organ class and MedDRA preferred term. On-study lab parameters including hematology, chemistry, liver function, thyroid function, and renal function will be summarized using worst grade per NCI CTCAE v4.0 criteria.

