**ADVERSE EVENTS**

Adverse Event Definition:
An Adverse Event (AE) is defined as any new untoward medical occurrence or worsening of a preexisting medical condition in a clinical investigation participant administered study drug and that does not necessarily have a causal relationship with this treatment.
An AE can therefore be any unfavorable and unintended sign (such as an abnormal laboratory finding), symptom, or disease temporally associated with the use of study drug, whether or not considered related to the study drug.

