7.5.5 Laboratory Parameters

The analysis population for each laboratory test is restricted to treated subjects meeting that laboratory test abnormality.

A summary as worst CTC grade on-treatment per subject and a by-subject listing of the following laboratory parameters abnormalities will be provided: hemoglobin, hematocrit, leukocytes, platelet count, ALT, AST, alkaline phosphatase (ALP), total bilirubin, lactate dehydrogenase, blood urea nitrogen (BUN) or serum urea level, creatinine, sodium, potassium, calcium, chloride, magnesium, creatinine clearance (CLcr), carbon dioxide or bicarbonate, amylase, glucose, phosphate, albumin, urinalysis labs, serology tests, FSH and lipase.

A summary and a by-subject listing of the following thyroid specific abnormalities will be provided: TSH, FT3, FT4.

A by-subject listing of differences in categorization of SI and US laboratory test results will be provided.

The analyses will be conducted using the 30-day safety window.

In addition, further analyses on specific laboratory parameters will be performed by treatment group:

Abnormal Hepatic Function Test

The number of subjects with the following laboratory abnormalities from on-treatment evaluations will be summarized:

- ALT or AST > 3 x ULN, > 5 x ULN, > 10 x ULN and > 20 x ULN
- Total bilirubin > 2 x ULN
- ALP > 1.5 x ULN
- Concurrent (within 1 day) ALT or AST > 3 x ULN and total bilirubin > 1.5 x ULN
- Concurrent (within 30 days) ALT or AST > 3 x ULN and total bilirubin > 1.5 x ULN
- Concurrent (within 1 day) ALT or AST > 3 x ULN and total bilirubin > 2 x ULN
- Concurrent (within 30 days) ALT or AST > 3 x ULN and total bilirubin > 2 x ULN

Abnormal Thyroid Function Test

The number of subjects with the following laboratory abnormalities from on-treatment evaluations will be summarized:

- TSH value > ULN and
 - with baseline TSH value \leq ULN
 - with at least one FT3/FT4 test value < LLN within 2-week window after the abnormal TSH test
 - with all FT3/FT4 test values \geq LLN within 2-week window after the abnormal TSH test
 - with FT3/FT4 missing within 2-week window after the abnormal TSH test.
- TSH < LLN and
 - with baseline TSH value \geq LLN
 - with at least one FT3/FT4 test value > ULN within 2-week window after the abnormal TSH test
 - with all FT3/FT4 test values \leq ULN within 2-week window after the abnormal TSH test
 - with FT3/FT4 missing within 2-week window after the abnormal TSH test

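### Apart from TSH, laboratory abnormalities are counted without the baseline value, so for ALT/AST >3x ULN, ALP and pancreatic-cohort lipase/amylase the counts cannot separate abnormality present at entry from abnormality arising on treatment

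*SAP*

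**What the plan says.** Protocol Table 4.-1 makes specific laboratory abnormalities, by worst grade, a component of the primary endpoint, next to AEs and SAEs. Protocol 10.3.2 states that on-study laboratory parameters "will be summarized using worst grade per NCI CTCAE v4.0 criteria". SAP 7.1.2 carries this out: "subjects will be counted only once for each lab parameter according to their worst on treatment CTC grade".

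SAP 7.5.5 adds a hepatic table of on-treatment values, including "ALT or AST > 3 x ULN, > 5 x ULN, > 10 x ULN and > 20 x ULN", total bilirubin >2x ULN, ALP >1.5x ULN, and four concurrent ALT/AST-plus-bilirubin rows. None of these has a baseline condition. The thyroid table in the same section does: high TSH has a sub-row "with baseline TSH value" at or below ULN, and low TSH has the mirror-image sub-row.

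SAP 6.1 defines a baseline laboratory evaluation, so the value is available. No shift table or worsening-from-baseline count is described, and SAP 7.2.2 does not list laboratory values among the baseline summaries.

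On entry, Protocol 6.1 criterion 2(j) limits AST and ALT to 3x ULN, or 5x ULN "if liver metastases are present". It contains no ALP criterion. Pancreatic participants with lipase or amylase above 1.5x ULN "may enroll if there are neither clinical nor radiographic signs of a pancreatitis", with no upper limit given.

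**The concern.** A participant with liver metastases who enters at AST 4x ULN and stays there is counted in the ALT/AST >3x ULN row at the first post-dose draw. A pancreatic participant with stable raised lipase is likewise summarized at whatever grade that value carries. Neither has changed on treatment.

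In a randomized trial the control arm would show how common this is. Here all participants were initially assigned to the combination (Protocol 7.2), so nothing in the design supplies the background rate, and no planned table shows the rate at entry. The matter is sharpest in the pancreatic cohort, the only one in which lipase and amylase are measured. At stake is whether the laboratory part of the tolerability endpoint can be read as change on treatment.

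**Working it through.** **Step 1: the plan's own safety figure.** Protocol 10.1 and SAP 5 say that 40 participants detect an event of 5% incidence with more than 87% probability. 1 - 0.95^40 = 0.8715, so the figure reproduces.

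**Step 2: which counts an unchanged participant can enter.** Planned counts are from SAP 7.5.5; entry limits are from Protocol 6.1, criterion 2(j).

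| Planned on-treatment count | Entry limit | Can an unchanged entry value be counted? |
|---|---|---|
| ALT/AST >3x ULN | 3x; 5x with liver metastases | Yes, with liver metastases and a value above 3x and up to 5x |
| ALT/AST >5x, >10x, >20x ULN | same | No |
| Total bilirubin >2x ULN | 1.5x; Gilbert syndrome <3.0 mg/dL | No, except possibly under the Gilbert exception |
| ALP >1.5x ULN | none | Yes |
| Four concurrent ALT/AST >3x with bilirubin >1.5x or >2x rows | both limits above | No, except possibly under the Gilbert exception |
| Lipase, amylase by worst grade (PAC) | none, absent signs of pancreatitis | Yes; the grade cannot be stated because CTC cut-offs are not in the documents |
| TSH >ULN, TSH <LLN | none | Yes, but a sub-row separates normal baseline |

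The hepatic table has 4 + 1 + 1 + 4 = 10 rows. Two are materially open: ALT/AST >3x ULN and ALP >1.5x ULN.

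**Step 3: illustration of size.** The documents give no baseline prevalence, so both inputs are assumptions. Let b be the share of a cohort over a threshold at entry, all staying over it, and t the new-onset rate among the rest. The denominator is all treated participants in the cohort.

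Reported rate R = b + (1 - b)t. Pre-existing share of those counted = b / R.

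| b (of 40) | R at t = 10% | Pre-existing share | R at t = 5% | Pre-existing share |
|---|---|---|---|---|
| 5% (2) | 0.05 + 0.95 x 0.10 = 14.5% | 34.5% | 9.75% | 51.3% |
| 10% (4) | 0.10 + 0.90 x 0.10 = 19.0% | 52.6% | 14.5% | 69.0% |
| 20% (8) | 0.20 + 0.80 x 0.10 = 28.0% | 71.4% | 24.0% | 83.3% |

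With no new onset at all (t = 0) and b = 5%, the chance that a cohort of 40 shows at least one counted participant is 1 - 0.95^40 = 87.15%. That equals the probability in Step 1 for a real 5% event. Seeing one or two such participants in these rows therefore does not by itself distinguish the two cases.

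**The case against.** The SAP implements the endpoint as the protocol words it, by worst grade. The protocol's AE definition, "any new untoward medical occurrence or worsening of a preexisting medical condition", governs AEs, which are a separate component of the endpoint. Laboratory results that are clinically significant, interrupt or stop treatment, or need corrective therapy are also captured as AEs (Protocol 9.2.6), so the laboratory table is not the only route. SAP 2.0 is a close-out plan for a synoptic report, with no p-values for efficacy and no decision rule based on laboratory incidence. By-subject listings of abnormalities are planned, and the Data Presentation Plan that holds the mock-ups is not available here.

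Most of this stands and limits the point. It does not supply the missing comparison with baseline: the SAP describes none outside TSH, and SAP 6.1 applies no subtracting rule to AEs either. A synoptic report that already carries detailed TSH and hepatic breakdowns can carry the extra rows.

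Stronger readings are tempting but not supported:
- A reader might infer that the SAP reports pre-existing disease as toxicity of the combination. It labels these counts as on-treatment and attributes none of them to drug. The risk lies in how they are read.
- A reader might infer that baseline is never used, or that every hepatic row is affected. The TSH rows and the eligibility limits show otherwise.
- A reader might extend the argument to hemoglobin, which is accepted from 9.0 g/dL. Judging which grade that fills needs CTC cut-offs that the documents do not give.
- The absence of a ceiling for lipase and amylase concerns the level a participant may have, not how many participants have it.

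**Conclusion.** The point holds for ALT/AST >3x ULN in participants with liver metastases, for ALP, and for lipase and amylase in the pancreatic cohort. For these, the planned counts cannot separate abnormality that arose or worsened on treatment from abnormality present at entry, within a primary-endpoint component and without a control arm. The remaining ALT/AST rows are protected by eligibility, as are the bilirubin and concurrent rows outside the Gilbert exception, provided values do not move between screening and first dose.

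The size cannot be fixed from the documents. The 14.5-28% range rests on assumed entry prevalence of 5-20%, 10% new onset among the rest, and full persistence of entry abnormalities; if some resolve before the first on-treatment draw, the effect is smaller. Counts out of 40 suit the TNBC and PAC cohorts. They do not suit NSCLC, where the combination was discontinued before 20 participants had been treated (SAP, Schedule of Analyses). The change is worth making because it alters what the tables can show at almost no cost.

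**What to change.** In SAP 7.5.5, keep the worst-grade tables and add:

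- for each graded parameter measured both at baseline and on treatment, a baseline-grade by worst-on-treatment-grade shift table, and the number of subjects whose grade worsened from baseline;
- under ALT/AST >3x ULN, a sub-row for subjects with baseline ALT and AST ≤3x ULN;
- under ALP >1.5x ULN, a sub-row for subjects with baseline ALP ≤1.5x ULN.

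The sub-rows match the existing TSH layout. A bilirubin sub-row is not needed, because eligibility makes it nearly redundant. The restriction to parameters measured at both times matters because SAP 7.5.5 also lists creatinine clearance and FSH, which Protocol Table 9.4.4-1 marks as screening only. State the denominator for the new counts, since SAP 7.5.5 restricts the laboratory population to treated subjects meeting the abnormality.

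The cost is SAP wording and standard programming. Baseline chemistry is already required within 14 days before first dose, so no new data are needed.
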